5.2.2.2 Exclusion criteria

- Serious disease or disease requiring teratogenic treatment (e.g., Lupus Erythematosus, Multiple Sclerosis, cancer)
- Multifetal pregnancy
- More than four (4) previous IVF embryo transfers
- Previous exposure to dydrogesterone in index pregnancy
- Documented substance abuse
- Treatment with hormones known to cause malformations. Participation in an observational study that might, in the recruiting HCP's opinion, influence the assessment for the current study
- Participation in a randomized clinical trial in the last 3 months
- Previous enrollment in the PEARLY study

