5.1 Study design

The PEARLY study is a prospective, observational, multi-center, multi-country, active surveillance registry study.

Different populations (based on different indications) will be included in the study with different subsequent analyses and separate data collection/follow-up for each of the cohorts of interest (see [Figure 1](#)). The different indication areas of interest include:

Cohort A: bleeding in early pregnancy/recurrent pregnancy loss

Cohort B: IVF/ART

A comparison of live birth rates and rate of major malformations in fetus and newborns will be based on indication area and by treatment (dydrogesterone, other progestogens, or other treatment).

[figure not shown]
Primary analyses focus on the rate of major malformations with exposure in the first trimester of pregnancy to:

- (1) Dydrogesterone versus non-dydrogesterone treatment

For the primary analysis, study participants taking any dydrogesterone preparation during the first trimester of pregnancy (at any time regardless of dosage and duration) as mono-treatment will be considered in the dydrogesterone group. Study participants taking at least one non-dydrogesterone preparation during the first trimester of pregnancy (at any time regardless of dosage and duration) as mono-treatment (i.e. no combination with dydrogesterone or another non-dydrogesterone) will be considered in the non-dydrogesterone group.

Further subgroups regarding specific dosage and duration will be considered in subgroup analyses.

Figure 1: Study Design

DYD: dydrogesterone, EDD: Estimated Date of Delivery, FU: follow-up, W: week, REOS: Regular End Of Study

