5.2.1 Selection of the Study Population

Study participants will be enrolled by recruiting HCPs. The recruiting HCPs are not necessarily involved in the subsequent follow-up (FU) of study participants. The recruiting HCP's role is to explain the nature of the study, its purpose and associated procedures, and the expected duration of follow-up for each study participant prior to their entry into the study.

Potential study participants will be identified by recruiting HCPs following initiation of progestogen or other treatment within the first trimester of pregnancy. Study participants will be recruited based on the inclusion and exclusion criteria as defined in section 5.2.2. Study population. As this is an observational registry study, the decision to prescribe dydrogesterone or other treatment is solely at the discretion of the HCP and the study participant. Study participants will continue to be managed throughout the study according to their HCP's prescribed treatment and will not be allocated to a study intervention.

Study participants will have the opportunity to ask questions and will be informed about their right to withdraw from the study at any time without disadvantage and without having to provide reasons for their decision. This information will be provided during the consenting process. Participation to the study is only possible if the informed consent and data privacy form is signed by the study participant. Once enrolled, a study participant may discontinue (and restart) treatment or may switch to another treatment as advised by the HCP at any time. However, study participants will continue to be followed whether or not they remain on the prescribed treatment, provided that they do not withdraw their consent.

Data will be collected directly from the study participants through electronic patient-reported outcome (ePRO) questionnaires. This means that study participants will be followed by ZEG Berlin independent of the HCP and follow-up is not necessarily linked to a clinical office visit. ZEG Berlin will obtain permission from the study participant to contact *any* treating or diagnosing HCP for clarification of a reported medical events (e.g. major malformations) during the study's observation time.

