5.2.2 Study population

Subjects receiving treatment with any progestogen, including dydrogesterone, or other treatment in the first trimester of pregnancy following; (A) a diagnosis of early bleeding in pregnancy or recurrent pregnancy loss, or (B) following IVF/ART embryo transfer will be eligible to be enrolled. The inclusion and exclusion criteria are defined in section 5.2.2.1. and section 5.2.2.2.

Subjects can be screened for the study only after an informed decision for dydrogesterone or alternative treatment has been made by the subject and the recruiting HCP. Indication and contraindications according to the local market authorization/ summary of product characteristics (SmPC) should be carefully considered by the HCP.

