5.2.2.1 Inclusion Criteria

- Pregnant women who wish to sustain their pregnancy
- Women who have tested positive (blood or urine) for pregnancy in the first trimester, seeking medical treatment
- Aged 18 – 35 years

AND

- Early bleeding in pregnancy with evidence of an intrauterine pregnancy / unexplained recurrent pregnancy loss (with ≥ 2 previous pregnancy losses) with evidence of an intrauterine pregnancy with visible gestational sac

OR

- Having undergone IVF/ ART embryo transfer and taking progestogen for luteal phase support (LPS), with evidence of an intrauterine pregnancy with visible gestational sac

OR

- Without taking a progestogen and advised an alternative treatment, in context of bleeding in early pregnancy, recurrent pregnancy loss, or undergoing natural cycle frozen embryo transfer (NC-FET)

AND

- Signed informed consent, allowing consent to contact all treating, or diagnosing HCP
- Able and willing to read and comprehend written instructions; comprehend and complete the questionnaires required by the protocol.

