5.5 Study size

Two independent cohorts will be considered in the analysis: (A) study participants with bleeding in early pregnancy and/or recurrent pregnancy loss and (B) study participants receiving IVF / ART. Sample size calculations for both cohorts are similar as based on an incidence proportion of major malformation at birth of 200 per 10,000 births for both indications [10–14]. It is expected that dydrogesterone is associated with a risk of major malformation that is not higher than the risk associated with non-use of dydrogesterone. The study is powered to test the non-inferiority of dydrogesterone treatment.

Assuming a drop-out rate of 20% and a rate of major malformation in fetal newborn of 0.02, sample size calculations show that approximately 5,500 study participants per cohort are statistically sufficient (power = 90%, one-sided $\alpha = 0.025$) to exclude a 2.0-fold risk (Odds Ratio) in the dydrogesterone cohort. The test statistic used is the one-sided Score test [15].

Table 1 and Table 2 show proposed sample sizes for sub-group specific allocation rates.

Cohort A: bleeding in early pregnancy / recurrent pregnancy loss

Table 1: Group allocation: 30% (dydrogesterone) versus 70% (reference)

Endpoint	Incidence proportion		Non-inferiority OR	Effective sample size		20%-Drop-out inflated sample size	
	Reference	DYD		Reference N ₁	DYD N ₂	Reference N ₁	DYD N ₂
Major malformation	0.02	0.02	2.0	3,136	1,343	3,920	1,679

Cohort B: IVF/ART

Table 2: Group allocation: 50% (dydrogesterone) versus 50% (reference)

Endpoint	Incidence proportion		Non-inferiority OR	Effective sample size		20%-Drop-out inflated sample size	
	Reference	DYD		Reference N ₁	DYD N ₂	Reference N ₁	DYD N ₂
Major malformation	0.02	0.02	2.0	2,059	2,059	2,574	2,574

The total number of study participants will be 11,000 across all geographical study sites China, Turkey and Russia.

Sample size has been calculated using the Statistical Software PASS 2021 Power Analysis & Sample Size [16].

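### The exclusion for previous dydrogesterone exposure has no reference point and conflicts with enrolment of women already on dydrogesterone

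*Protocol*

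**What the plan says.** The exclusion list in Protocol 5.2.2.2 contains "Previous exposure to dydrogesterone in index pregnancy". It gives no time window, no indication, and no wording that limits it to an earlier course. No other section defines the term.

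Four other places bear on when a woman enters and what she may be taking:

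- **5.2.1:** "Potential study participants will be identified by recruiting HCPs following initiation of progestogen or other treatment within the first trimester of pregnancy".
- **5.2.2, eligible population:** "Subjects receiving treatment with any progestogen, including dydrogesterone, or other treatment in the first trimester of pregnancy".
- **5.2.2, screening:** "Subjects can be screened for the study only after an informed decision for dydrogesterone or alternative treatment has been made". The abstract likewise places recruitment after the treatment decision.
- **5.2.2.1, cohort B luteal-support branch:** "Having undergone IVF/ ART embryo transfer and taking progestogen for luteal phase support (LPS), with evidence of an intrauterine pregnancy with visible gestational sac".

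The variables table in 5.3.2.4 records treatment start and duration at baseline, which fits women already on treatment. It also re-asks two items at the first follow-up for IVF/ART women who were not yet pregnant when they entered.

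For the primary analysis, 5.1 places in the dydrogesterone group "study participants taking any dydrogesterone preparation during the first trimester of pregnancy (at any time regardless of dosage and duration) as mono-treatment".

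**The concern.** A woman who enters on dydrogesterone has, by then, been exposed to dydrogesterone in the index pregnancy. The feature that qualifies her for the exposed group also meets the exclusion as worded. A screener cannot apply 5.2.2.2 word for word and also enrol the women whom 5.2.1, 5.2.2 and 5.2.2.1 describe.

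The rule also acts on one side only, since earlier use of another progestogen is not an exclusion. If practitioners in three countries resolve the conflict differently, entry to the study depends on dydrogesterone exposure and on how long after first intake a woman is seen. Section 5.9 relies on selection differences being alike across the compared groups, and a screening rule tied to the study drug alone works against that assumption.

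**Working it through.** This is a check of consistency. The plan gives no figure for the effect of this criterion. The only arithmetic is the number of women concerned.

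**1. Planned dydrogesterone numbers (5.5, Tables 1 and 2).** The inflation is N / (1 − 0.20):

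- Cohort A: 1,343 / 0.80 = 1,678.75, rounded up to 1,679. This matches Table 1.
- Cohort B: 2,059 / 0.80 = 2,573.75, rounded up to 2,574. This matches Table 2.
- Together: 1,679 + 2,574 = 4,253 women.

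**2. Typical women set against the text.** The *literal* column takes any dydrogesterone intake before enrolment as previous exposure. The *earlier course* column takes only intake before the current treatment course.

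| Woman at entry | Inclusion and entry wording | Exclusion, literal | Exclusion, earlier course |
|---|---|---|---|
| Cohort B, on dydrogesterone luteal support, sac visible | Meets 5.2.1, 5.2.2, 5.2.2.1 | Excluded | Eligible |
| Cohort A, dydrogesterone already started | Meets 5.2.1, 5.2.2 | Excluded | Eligible |
| Cohort A, dydrogesterone decided, not yet taken | Meets the screening wording in 5.2.2, not the post-initiation wording in 5.2.1 | Eligible | Eligible |
| IVF/ART, not yet pregnant (5.3.2.4) | Fails 5.2.2.1, which requires pregnancy | Not triggered | Not triggered |
| Stopped dydrogesterone and restarted before entry | Meets 5.2.1, 5.2.2 | Excluded | Unclear |
| On another treatment now, dydrogesterone earlier in this pregnancy | Meets 5.2.1, 5.2.2 | Excluded | Excluded |

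**3. What the table shows.** In the first two rows, following the text word for word turns away women whom other sections declare eligible. The third and fourth rows show a second inconsistency: the protocol does not fix a single time of entry. It could be after the decision, after initiation, or, for some IVF/ART women, before pregnancy. The fifth row shows that even the sympathetic reading leaves cases open. Section 5.2.1 lets enrolled women stop, restart and switch, so the same treatment history may be allowed or barred depending only on the date of enrolment.

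**4. Could the group be filled another way?** A woman who enters on another progestogen and later changes to dydrogesterone would not count, because 5.1 requires mono-treatment. Under the literal reading, the remaining route is entry before first intake. The cohort B luteal-support branch closes that route for its own women by requiring current use.

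**5. Is the criterion needed to keep the primary groups clean?** In the last row, 5.1 already leaves a woman with both exposures in the first trimester out of both mono-treatment groups. For the primary comparison the exclusion adds little that the group definition does not already do.

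**The case against.** The strongest reply is that nobody would read the criterion as barring the drug under study. Section 5.2.2 names dydrogesterone users as eligible, 5.1 defines a dydrogesterone group, and 5.5 plans for 30% and 50% dydrogesterone shares. In ordinary use *previous* means before the present treatment. Section 5.8 provides for training recruiting practitioners before the first patient enters and for monitoring recruitment by treatment group. The screening form is not part of the protocol and may already apply the criterion sensibly.

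Most of this stands. The intent is very probably an earlier course, and training and monitoring would catch a gross failure. What remains is that the protocol does not state that intent, the open cases above are not settled by it, and the screening form takes its authority from this text.

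A reader might infer stronger things that the documents do not support:

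- **That none of the 2,574 cohort B users, or no dydrogesterone user at all, could enrol.** Cohort A women enrolled between decision and first intake stay eligible, and 5.3.2.4 contemplates some IVF/ART women entering before pregnancy.
- **That power falls to 78%.** With 5,500 × 0.80 = 4,400 evaluable cohort A women, a 2% rate in both groups, an odds-ratio margin of 2.0 and one-sided 0.025, exact score-test power is 86.9% at a 30% dydrogesterone share (1,320 / 3,080) and 78.0% at 20% (880 / 3,520). The 20% share has no source in the protocol. The figures show sensitivity to an assumed share, not the effect of this criterion.
- **That the bias is beyond repair.** Treatment start, treatment duration and weeks since last menstrual period are collected at baseline, so the interval from initiation to entry can be examined in enrolled women. Adjustment cannot by itself recover women turned away at screening, but how many there would be is conjecture.

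**Conclusion.** The contradiction is real and is in the current text. As worded, the exclusion catches cohort B women who enter on dydrogesterone luteal support and cohort A women enrolled after first dydrogesterone intake, while three other sections make those women eligible. It does not catch cohort A women enrolled after the decision but before first intake. The mention in 5.3.2.4 of IVF/ART women not yet pregnant is a further inconsistency about time of entry.

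The rule bears on a planned 4,253 dydrogesterone users, but that is the size of the group concerned, not a forecast of losses. If the intent is exposure before the current course, as seems likely, the practical risk is that practitioners and countries screen differently, in a way that depends on the exposure under study. Any consequent loss of power is hypothetical. The conclusion rests on the wording alone and on no assumed rate or allocation.

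**What to change.** Reconcile 5.2.1, 5.2.2, 5.2.2.1, 5.2.2.2 and 5.3.2.4. There are two coherent ways to deal with the exclusion:

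- **Define it.** State one time of entry and say what *previous* refers to, so that the dydrogesterone treatment that qualifies a woman for the study does not itself trigger the exclusion. Say how women who stopped and restarted before entry are classed. The sponsor must supply the intended meaning.
- **Delete it.** The first-trimester mono-treatment definition in 5.1 already keeps mixed exposure out of the primary groups. This presumes that 5.1 governs: 5.7.2 mentions treatment combinations in the comparator while deferring to 5.1. The time of entry still needs to be stated once.

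In either case, align the participant screening form and the practitioner training with the chosen wording. The cost is a one-line amendment to the criterion, with matching edits on time of entry, and a check of one screening item. Sample size and analysis model are unaffected.

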5.2.2.3 Withdrawal / drop-out / lost to follow-up (LTFU)

Study participants can refuse to further participate, or may withdraw from the study, at any time and without giving a reason. As this is an observational study, withdrawal from the study is independent of the underlying therapy and will not affect medical care.

If a study participant wishes to terminate study participation, no further data will be collected. Data which were collected prior to withdrawal may be used in the data analysis for the purpose of this study. In case a study participant would like to withdraw the consent given earlier, the withdrawal should be documented in the electronic Case Report Form (eCRF) in the EDC solution by MediData. Study participants who withdraw from the study prior to regular study end will be included in drop-out numbers.

Study participants who experience a spontaneous abortion or pregnancy termination during study conduct will not receive further follow-up (FU) questionnaires. These study participants are considered to have reached regular end of study (REOS) after completion of the follow-up questionnaire in which the spontaneous abortion or pregnancy termination was reported.

A study participant becomes lost-to-follow-up (LTFU) when the study questionnaire(s) are no longer completed and re-contact attempts remain unsuccessful. To limit LTFU, ZEG Berlin will implement a well-established active-surveillance (AS) methodology. Automatic reminders (e.g., e-mail) to complete study questionnaires will be issued via the ePRO solution by MediData. In case of ongoing non-response, further manual contact attempts (e.g., telephone) will be initiated by the local field organizations team.

Participants will not be replaced after drop-out or LTFU.

5.2.3 Validation of Self-Reported Events

A self-administered questionnaire used by study participants at short intervals is a sensitive tool which captures almost all serious clinical outcomes [8]. From a methodological point of view, it captures a much higher proportion of these outcomes than methods relying only on the prescribing HCP who may not be involved in the diagnosis and treatment of these outcomes. However, there is a significant difference between the rates of patient-reported and medically confirmed events after validation as laypersons often misclassify adverse events, therefore, assessment of the self-reported events is of utmost importance.

In this study, self-reported events considered as a defined primary outcome, i.e., major malformations defined in section 5.3.1 will be validated with the goal to identify if the reported event was medically confirmed.

The follow-up questionnaires (ePRO) will be programmed with specific constraints allowing for additional questions to be displayed if a potential major malformation is reported by a study participant. Questionnaires with a potential major malformation are automatically flagged and transferred to the medical event validation team at ZEG Berlin. The medical event validation team will work within the EDC solution to validate all events considered as a primary study outcome. During the validation process it may be necessary to re-contact the study participant or diagnosing and/or treating HCP for validation of the information initially received from the study participant to, a) clarify information and b) obtain additional information for medical confirmation of the event. All additional data gathered during this procedure is entered into the eCRF EDC solution by ZEG Berlin. Further details will be described in the Data Management Working Procedures.

ZEG Berlin will oversee the outcome validation process by asking the local field organization to contact the study participant and/or HCP to gather more necessary information. The field organization then will contact the study participant and/or HCP in the local language. The field organization will provide the medical documentation and an English translation to ZEG Berlin for further processing.

Under routine medical conditions, diagnosis of a disease/condition is not always confirmed by a diagnostic method with high specificity. Therefore, the primary study outcomes will be classified by ZEG Berlin's medical event validation team according to a predefined algorithm which will be further specified in the working procedures. The data is captured by ZEG Berlin's medical event validation team in the eCRF section for event validation.

- **Definite Event:**
Diagnosis confirmed by diagnostic measures with high specificity or written proof available e.g., medical record.
- **Probable Event:**
Absence of confirmation by a diagnostic measure with high specificity for the diagnosis, but clinical diagnosis confirmed (verbally or in writing) by an HCP or supported by diagnostic tests with low specificity.
- **Possible Event:**
Condition considered as primary outcome was reported by the study participant only and no confirmation could be obtained to prove or disprove the event or no diagnostic measures were performed that could have clarified the diagnosis.
- **Event not confirmed:**
Diagnosis reported by the study participant is excluded by diagnostic procedures.
A different medical condition is diagnosed by the attending HCP.

